8.4. Anticipated Adverse Events and Complications

Complications and anticipated adverse effects associated with SCS implantation include but are not limited to:

- Stimulation at high outputs may cause unpleasant sensations or motor

disturbances, including involuntary movement. If either occurs, turn off your IPG immediately.

- Undesirable changes in stimulation may occur over time. These changes may be related to cellular changes in tissue around the electrodes, changes in electrode position, loose electrical connections, and/or lead failure.
- Stimulation may occur in unwanted places, such as the radicular (nerve root) chest wall area
- A lead can move and result in changes in stimulation and/or a reduction in pain relief
- Placement of a lead in the epidural space may cause epidural hemorrhage, hematoma, infection, spinal cord compression, and/or paralysis
- Cerebrospinal fluid (CSF) leakage is possible
- Paralysis, weakness, clumsiness, numbness, and/or pain below the level of the implant can occur
- Persistent pain may occur at the electrode or IPG site
- Seroma (mass or swelling) may occur at the IPG site
- Implant materials may cause an allergic or rejection response
- The implant can move, or skin can erode from around it
- Battery failure and/or battery leakage is possible

IPG Complications

Changes in stimulation parameters may occur due to the failure of, or changes in, components over time, which results in:

- Understimulation
- Return of underlying symptoms
- Overstimulation
- Premature battery depletion, and
- The need to explant the device

8.5. AE Classification

The Investigator will classify each adverse event. If the adverse event is serious or the Investigator feels that the device contributed in any way to the adverse event, the Investigator must report the event to the IRB.

8.5.1. Severity Rating

The Investigator will use the following definitions to assess the severity of the adverse event to the device/procedure:

A MILD adverse event is an event that causes awareness of signs or symptoms, but easily tolerated; are of minor irritant type; causing no loss of time from normal activities; symptoms would not require medication or a medical evaluation; signs and symptoms are transient.

A MODERATE adverse event is an event that causes discomfort severe enough to cause interference with usual activities; persistent or requiring treatment.

A SEVERE adverse event is an event severe enough that causes an inability to perform normal, daily activities; persistent or requiring treatment.

8.5.2. Relationship to Device/Procedure

An adverse event where the causal relationship to the device and/or procedure has been classified as *possibly*, *probably*, or *definitely*, the relationship must meet the NIH definition for relatedness of an adverse event to an intervention as follows:

- *Possibly* Device/Procedure-Related: (must meet at least 2 criteria)
 - 1) Has a reasonable temporal relationship to intervention,
 - 2) Could not readily have been produced by the patient's clinical state,
 - 3) Could not readily have been due to environment or other interventions,
 - 4) Follows a known pattern of response to intervention.
- *Probably* Device/Procedure -Related: (must meet at least 3 criteria)
 - 1) Has reasonable temporal relationship to intervention,
 - 2) Could not readily have been produced by the patient's clinical state or have been due to environmental or other interventions,
 - 3) Follows a known pattern of response to intervention,
 - 4) Disappears or decreases with reduction in dose or cessation of intervention.
- *Definitely* Device/Procedure -Related: (must meet all 4 criteria)
 - 1) Has a reasonable temporal relationship to intervention,
 - 2) Could not readily have been produced by the patient's clinical state or have been due to environmental or other interventions,
 - 3) Follows a known pattern of response to intervention,
 - 4) Disappears or decreases with reduction in dose or cessation of interventional and recurs with re-exposure.

9. Data Review and Database Management

9.1. Site Monitoring

Before study initiation at any sub-sites, the sponsor-investigator, or designee, will review the protocol and CRFs with the investigators and their staff, and protocol training will be documented

The investigator must maintain source documents for each patient in the study, consisting of case and visit notes (hospital or clinic medical records) containing demographic and medical information, laboratory data, and the results of any other tests or assessments. All information on CRFs must be traceable to these source documents in the patient's file. Data not requiring a separate written record will be defined before study start and will be recorded directly on the CRFs. The investigator must also keep the original informed consent form signed by the patient (a signed copy is given to the patient).

SJM will monitor all sites according to their own internal standard operating procedures.

No information in source documents about the identity of the patients will be disclosed.

9.2. Data Collection

Designated investigator staff must enter the information required by the protocol onto the paper CRFs, and copies of the patient questionnaires will be sent to SJM. SJM will send a

monthly enrollment and CRF report to all investigators.

9.3. Database Management and Quality Control

Data from the patient questionnaires and CRFs will be reviewed by SJM following their own internal standard operating procedures.

Errors or omissions on paper CRFs will generate queries that will be returned to the investigational site for resolution. Quality control audits will be completed by SJM as needed, and prior to finalizing data.

SJM will send an updated database of all data on a quarterly basis unless the enrollment accelerates, in which case, SJM will send an updated database with the monthly enrollment/CRF report.

10. Data Analysis

10.1. Statistical Plan

The study design for this investigation is a post-market, prospective, multicenter, parallel design, non-blinded study with primary analysis at 24 weeks. The primary objective in this study is to demonstrate the effectiveness and safety of the non-awake procedure compared to the awake procedure.

10.2. Sample Size Justification

Recent, retrospective studies of single center experience with the two procedures suggests the following complication and repositioning rates and procedure time (Falowski et al., 2011; Shils & Arle, 2012);;

Table 2: Outcome rates for sample size calculation

	Non-awake	Awake
Revisions for device failure	15%	30%
Lead repositioning for efficacy	1%	15%
Infection rate	4.5%	6.0%
Procedure time	60 minutes	90 minutes

Simulations based on these results indicated that the sample size required to reject the null hypothesis at the 5% significance level is a minimum of 50 patients, who will be enrolled 1:1 between the two procedures. Note that because neither procedure is currently considered the “gold standard”, and given the primary research objective of assessing safety and efficacy, it was determined that the sample size calculation should not be based on a formal hypothesis of non-inferiority with a pre-determined non-inferiority margin.

Sample Size Adjustments - Patients have already been approved for a permanent system implant, thus a screen failure rate of 0% is assumed. The objective of the study is to study the implant procedures, eliminating the need to account for non-responders to treatment.

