Randomization:	There will be no randomization of the patients. Patients recruited and enrolled at St. Luke's Neurological Associates or Thomas Jefferson University will undergo implantation under general anesthesia with EMG neuromonitoring for testing of the distribution of induced paresthesia ("non-awake"). Patients recruited and enrolled at Geisinger or Milton S. Hershey Medical Centers will undergo implantation of the device in an awake operation with local anesthetic and patient interaction for testing of the distribution of the induced paresthesia ("awake").
Statistical Analysis:	The primary endpoints will be procedure time, rates of adverse events, specifically lead revisions, and patient satisfaction. An additional endpoint will be the proportion of painful regions covered by paresthesia in non-awake compared to awake patients
Adverse Events	All device/procedure-related and all serious adverse events that occur and are volunteered by the patient and solicited by the site staff will be collected.

1. Introduction

Spinal cord stimulation (SCS) is an adjustable, non-destructive, therapy in which an electrical current is applied to the spinal cord for management of neuropathic pain. Leads are placed in the epidural space, which apply electrical stimulation to the spinal cord. It has been used for many years and has proven to be effective in the treatment of chronic, intractable pain including failed back surgery syndrome CRPS, phantom limb pain, cancer pain, peripheral vascular disease, and ischemic limb pain (Burchiel et al., 1996; Cameron, 2004; Kemler, de Vet, Barendse, van den Wildenberg, & van Kleef, 2008; Khan, Raza, & Khan, 2005; Turner, Loeser, Deyo, & Sanders, 2004).

The success of the therapy relies on the ability to create an overlap between the pain areas and the device-induced paresthesia. Lead placement has historically been done under awake conditions, using direct feedback from the patient in order to define adequate paresthesia coverage. The awake operation is performed while the patient is under local anesthesia, which is very stressful for the patient and predisposes them to movement. This can lead to decreased patient satisfaction, equipment migration, undesired stimulation effects, and treatment failure.

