Implantation under general anesthesia using electromyography (EMG) responses to determine paresthesia coverage may offer advantages over the awake procedure. This “non-awake” technique is potentially more comfortable for the patient and may carry less risk for revision. Recently, several retrospective studies have found that the non-awake procedure is safe and at least as efficacious in producing adequate paresthesia coverage as the awake procedure (Air, Toczyl, & Mandybur, 2012; Falowski et al., 2011; Shils & Arle, 2012). Falowski et al. found that the non-awake procedure resulted in the same or fewer revisions as the awake procedure. Shils observed a 30 minutes (33%) reduction in procedure time.

These studies are promising, yet there is a need for a prospective study to determine the equivalency or benefit of the non-awake procedure. The purpose of the proposed clinical study is to collect data necessary to demonstrate the safety and efficacy of non-awake implantation of SCS paddle leads compared to the awake procedure. The study is designed to evaluate whether non-awake placement reduces procedure time, complication rates, and/or revision rates while offering comparable paresthesia coverage as the awake procedure.

2. Objectives/Endpoints

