7.7. Postoperative Management and Instruction

The physician will provide normal standard of care after implantation of the system, including standard post-operative monitoring. Instructions for wound care and monitoring will be provided to the patient by the implanting physician. Patients will be informed to report any adverse events or changes in medication to study personnel. Patients will be informed not to manipulate the leads after implantation because tissue erosion may occur. The patient will be sent home for a 2-3 week recovery period to let any swelling and/or post-operative pain subside prior to activation of SCS system, unless otherwise

determined by the installing investigator. During this time, the device may not be activated and the patient may not be provided with the Patient Programmer. Prophylactic antibiotic therapy may be instituted at the discretion of the Investigator.

If the leads migrate during the study, the implanting physician will examine the area of implantation. The leads can be repositioned or re-implanted if mutually agreed upon by the physician and the patient. The patient and the implanting physician will make the mutual decision about any possible revision of the device based upon what is medically safe, what is desired by the patient, and what is in the patient's best medical interests.

If an infection occurs, standard medical practice suggests that the leads be removed and the patients undergo a standard course of oral antibiotics. Any infection or wound will be given time to heal before any re-implantation is attempted.

If the device is completely explanted from the study patient for any reason and re-implantation is not an option, then the patient will exit the study.

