10.3.3. Procedure Time

Hypothesis:

The non-awake is comparable to the awake method in the number of revisions

Metrics:

Rate of revisions (percentage of patients with a revision)

Statistical Tests:

Chi-square or Fisher's exact test as appropriate based on the number of adverse events
Significance at $\alpha < 0.05$, with no adjustment for the multiple comparisons.

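### Fifty patients do not give 80% two-sided power for the Table 2 differences in device-failure revisions, with or without lead repositioning, and a non-significant revision test cannot support comparability

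*Combined protocol and SAP*

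**What the plan says.** Section 10.2 lists four outcomes in Table 2, non-awake against awake: revisions for device failure (15% vs 30%), lead repositioning for efficacy (1% vs 15%), infection (4.5% vs 6.0%) and procedure time (60 vs 90 minutes). It then states that "the sample size required to reject the null hypothesis at the 5% significance level is a minimum of 50 patients", enrolled 1:1. It does not say which outcome that null hypothesis concerns. It explains that, since neither technique is the reference standard, no non-inferiority margin was used. Section 6 caps each arm at 30.

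Revisions are a primary variable in Section 2.3. The Protocol Summary singles them out among the primary endpoints ("rates of adverse events, specifically lead revisions"), and the Introduction says the study will evaluate whether non-awake placement "reduces procedure time, complication rates, and/or revision rates". Section 10.3.3 (headed Procedure Time, but about revisions) gives the hypothesis "The non-awake is comparable to the awake method in the number of revisions", the metric "Rate of revisions (percentage of patients with a revision)", and a chi-square or Fisher's exact test at 0.05. Section 10.3.2 does the same for adverse events.

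What counts as a revision is not fixed. Table 2 keeps "Lead repositioning for efficacy" in its own row. Section 7.7 says "The leads can be repositioned or re-implanted if mutually agreed upon by the physician and the patient" and goes straight on to "the mutual decision about any possible revision of the device". It also describes removing infected leads, with re-implantation possible later.

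**The concern.** Read together, Table 2 and the sentence after it suggest that 50 patients are enough for the outcomes in the table, including the revision difference. For revisions that does not follow.

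The hypothesis makes this matter more. Sections 10.3.2 and 10.3.3 state that the methods are comparable, yet the planned tests can only reject equality. With low power, a non-significant result is likely even when the awake revision rate is twice the non-awake rate. Nothing in Sections 10.2 to 10.6 says how such a result is to be read, so a missed difference could be taken as support for the stated hypothesis.

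**Working it through.** **Inputs.** Rates and mean times from Table 2; 25 per arm (50 at 1:1, Section 10.2) and 30 per arm (Section 6); alpha 0.05 and chi-square or Fisher (Section 10.3.3). Assumed, because the plan is silent: two-sided testing of proportions, the overlap between Table 2 rows, the SD of procedure time, and 80% as the power benchmark.

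**1. Can 50 be reproduced?** Not from the stated inputs, since endpoint, power and SD are absent. For a proportion, n per arm = [1.96·√(2p̄(1−p̄)) + 0.842·√(p₁(1−p₁)+p₂(1−p₂))]² / (p₂−p₁)². For 15% vs 30%, p̄ = 0.225 and n = (1.157 + 0.489)² / 0.0225 ≈ 121, a total of 242.

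For procedure time, 80% power for a 30-minute difference needs a total of 48 at SD 37 and 52 at SD 38. Noncentral-t power at 25 per arm is 93% (SD 30), 80% (SD 37), 74% (SD 40) and 55% (SD 50). So 50 is consistent with procedure time at an SD near 37 minutes, which the plan does not give.

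**2. Readings of revision.**
- A, device failure only: 15% vs 30%. If every repositioned patient also has a device-failure revision, the combined rate is the same.
- B, both rows, independent: 1 − 0.85×0.99 = 15.85% vs 1 − 0.70×0.85 = 40.5%.
- C, both rows, additive: 16% vs 45%.
- D, most favourable overlap of the two rows (complete in the non-awake arm, none in the awake arm): 15% vs 45%.

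**3. Power.** For each pair of event counts (x, y), I multiplied the two binomial probabilities and summed the products over the pairs with two-sided p < 0.05. The bracketed value uses Fisher only when an expected count is below 5.

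| Reading | 25 per arm: Fisher always to chi-square (mixed) | 30 per arm: Fisher to chi-square | Total N for 80% |
|---|---|---|---|
| A | 15.0% to 25.7% (24.3%) | 19.2% to 28.1% | 242 |
| B | 36.7% to 51.4% (51.1%) | 46.9% to 57.5% | 104 |
| C | 49.4% to 63.5% (63.4%) | 60.4% to 70.0% | 78 |
| D | 53.0% to 67.1% (67%) | 64.5% to 73.7% | 72 |

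All four totals exceed 60, the most that two arms of 30 allow.

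**4. Chance of a non-significant test at 25 per arm** (100% minus power, chi-square to Fisher): A 74.3% to 85.0%; B 48.6% to 63.3%; C 36.5% to 50.6%; D 32.9% to 47.0%.

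**5. Precision.** The expected half-width of a Newcombe 95% interval for the difference at 25 per arm is 22.2, 22.9 and 23.0 points for A, B and C. The interval would show how little a non-significant result rules out.

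**6. Adding infection-related surgery.** Independent rows give 19.64% vs 44.07%, with power 34.6% to 47.9% at 25 per arm and 42.9% to 53.1% at 30. Additive rows (20.5% vs 51%) give 52.5% to 65.0% and 60.8% to 70.3%. The most favourable overlap of all three rows (15% vs 51%) gives 70% (Fisher) to 81% (chi-square) at 25, and 80% to 86.5% at 30.

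**The case against.** The strongest reply is that 50 was never claimed to suffice for revisions. Section 10.2 states no power and does not name that endpoint. The Introduction's wording, which joins procedure time, complications and revisions with an and/or, fits a rule that any one of them would do. This stands: a reader might infer that 50 is a miscalculation, but the documents do not support that.

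A reader might also infer that no definition of revision could reach 80%. That goes too far. Counting infection-related surgery with the extreme overlap in step 6 reaches 81% by chi-square at 25 per arm. One-sided chi-square testing at 30 per arm reaches 80.6% for 16% vs 45% (72% by Fisher). Section 10.3.3 does not state sidedness, but an ordinary chi-square test is two-sided and the t-tests in Section 10.3.1 are explicitly so.

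The low ends of the ranges assume Fisher always. If Fisher is kept for small expected counts, as the plan's wording suggests, power lies close to the chi-square end: 24% rather than 15% for device failure. That too is far below 80%.

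Finally, declining a margin was a disclosed choice with a reason, and no passage says that non-significance will be read as comparability. Both points are fair. The misreading is a risk left open, not a stated plan. But a difference test without a margin still cannot support the hypothesis written in Section 10.3.3.

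**Conclusion.** The point holds for revisions, not for the sample size as a whole. With two-sided 5% tests and revision taken as device failure with or without lead repositioning, none of the four readings reaches 80% power at 25 per arm or at the cap of 30, where the best is 74%. If Table 2 is right, the Section 10.3.3 test is non-significant in 74% to 85% of studies (device failure only) or about 33% to 63% (readings B to D). Such a result cannot support comparability, and the same logic applies to adverse events in Section 10.3.2, where power cannot be computed because no overall event rate is given.

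The conclusion rests on the Table 2 rates, two-sided testing, the assumed overlap patterns and full follow-up. Section 10.6 restricts the analysis to patients who complete the 6-week visit, and Section 10.2 makes no dropout allowance, so losses from a given enrolment would lower these powers. The plan should be changed, but in wording only.

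**What to change.** Keep the sample size as it is.

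1. In Section 10.2, tie 50 only to the endpoint or decision rule that the simulations used, and add: *The study is not powered to detect the Table 2 differences in revisions.*
2. In Section 10.3.3, state whether revision includes lead repositioning for efficacy and infection-related surgery, and give the two-sided power that matches that definition. Settle this before the data are analysed.
3. In Sections 10.3.2 and 10.3.3, add: *The difference in proportions will be reported with its 95% confidence interval. A non-significant test will not be read as showing that the methods are comparable.*

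This costs no patients. The sponsor must go back to the simulation record, and the stated justification becomes less favourable.

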3.1. Design

This is a post-market, prospective, multicenter, parallel designed, non-randomized, non-blinded, 6-month study. A minimum of 50 patients will be implanted from up to 4 active sites, coordinated by a single lead investigator.

Patients who have had a successful SCS trial and are indicated for permanent implantation will be approached to participate in this study prior to permanent implantation. Patients will be recruited and enrolled by physicians at any one of the involved sites. Each Investigator will only use one method (awake or non-awake) according to his/her typical practice. Patients will receive treatment from their enrolling physician.

[figure not shown]

Table 1: Study Schedule

Timing of visit	Activities at visit	Case Report Forms
Screening and Informed Consent (may be immediately after Trial System Explant)	Patient evaluated for eligibility Patient signs informed consent Schedule patient for baseline evaluation at treatment site	Enrollment Form Inclusion/Exclusion Criteria Form
Baseline Evaluation 7-28 days after screening	Patient completes questionnaires Complete history and physical exam Record current medication use Collect patient reported data	Baseline Self Evaluation Form Pain Location Form Pain Evaluation Form SF-MPQ-2 (Pain Quality) EQ-5D (Quality of life) Medication Form
Permanent System Implantation	Permanent system implantation Record any complications Record any changes in medication Discourage activation at discharge Save digital recording or EMG recording if system permits.	Surgery Form Adverse Event Form Programming Form (if programmed at discharge) Medication Form
Initial Programming Visit	Record any complications Record any changes in medication Provide patient with the patient programmer and charging system Record patient's global impression of satisfaction with the implant procedure.	Programming Form Paresthesia Coverage Form Patient Global Impression Form Medication Form
6 weeks 42 ± 7 days after activation	Record any complications Record any changes in medication Patient completes questionnaires Modify programming parameters (if necessary) Collect patient reported data	Follow-up Visit Form Pain Evaluation Form Pain Location Form Programming Form SF-MPQ-2 (Pain Quality) EQ-5D (Quality of life) Paresthesia Coverage Form Medication Form

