10.3. Primary Analysis

10.3.1. Procedure Time

Hypothesis:

The non-awake method is faster than the awake method.

Metrics:

Skin-to-skin surgical time
Intraoperative programming time
Total fluoroscopy used (time and dose)

Statistical Tests:

Test for normality (such as Jarque-Bera)
Unpaired, two-sided Student's t-tests (normally distributed continuous data) or Mann-Whitney rank sums test (skewed continuous data)
Significance at $\alpha < 0.05$, with no adjustment for the multiple comparisons

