10.6. Data Sets

All patients who complete the 6 week follow-up appointment and questionnaires will be included in the analysis.

Patients with missing baseline values will be excluded from the analysis. Missing data pertaining to adverse events will not be imputed.

11. Withdrawal of Patients from Study

Withdrawal is defined as a patient’s termination of participation from a clinical study. Patients may be discontinued from the study at any time. The reason for discontinuation will be recorded

on the Exit and Withdrawal form. Discontinued patients may not be replaced in the study. Prior to discontinuing a patient, every effort should be made to contact the patient in an effort either to get the patient back into compliance with the protocol, or to obtain as much follow-up data as possible. Reasons for discontinuation include, but are not necessarily limited to:

- Voluntary withdrawal by the patient;
- Patient is Lost to Follow-up: Patient will be considered “lost to follow-up” after a minimum of 2 documented phone calls by personnel at the investigational center to the patient or emergency contact and a certified letter was sent to the last known address.
- Investigator may discontinue the patient’s participation in the study for reasons including but not limited to: patient noncompliance, surgical revision not appropriate, unwillingness or inability to cooperate with study requirements (therapy regimen, follow-up visits, etc.).

12. Modification of Protocol

Any amendments to this protocol must be prepared by the Coordinating Investigator and approved by the appropriate regulatory agencies and the local authority (IRB) before implementation by the Investigator.

13. Discontinuation of Study

The Clinical Coordinating Investigator reserves the right to discontinue any study at any time for administrative reasons, such as but not limited to, a decision to discontinue further clinical Investigations with the devices, improper conduct of the study by the Investigator, inability to obtain the number of patients required by the protocol, etc.

If the study is prematurely terminated or suspended, it is the responsibility of the investigator to promptly inform the patients and assure appropriate therapy and follow-up. The Investigator must also adhere to local IRB requirements and reporting of study termination or discontinuation.

14. References

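### Section 10.2 gives 50 patients as the required minimum with no allowance for attrition or missing data, while Section 10.6 analyses 6-week completers with baseline values and nothing requires 50 of them

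*Combined protocol and SAP*

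**What the plan says.** Section 10.2 reports, from simulations, that the number "required to reject the null hypothesis at the 5% significance level is a minimum of 50 patients". Allocation to the two methods is equal, which makes 25 per arm. Its paragraph on adjustments deals with two things. Because candidates are already approved for a permanent implant, "thus a screen failure rate of 0% is assumed"; and non-response to treatment is set aside because the implant procedure is the object of study. It does not mention dropout, missed visits or missing data.

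Four other places bear on how many patients reach the analysis:

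- Section 3.1 counts patients at surgery: "A minimum of 50 patients will be implanted". The protocol summary gives a population of about 50.
- Section 6 caps each arm at 30 enrolled, so 60 in all.
- Section 10.6 defines the one analysis set in the plan: "All patients who complete the 6 week follow-up appointment and questionnaires will be included in the analysis". Patients lacking baseline values are left out.
- Section 11 lists voluntary withdrawal, loss to follow-up and discontinuation by the investigator, and adds: "Discontinued patients may not be replaced in the study". Section 7.7 has a patient leave the study after complete explant when re-implantation is not an option.

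**The concern.** The plan states its requirement in one unit and secures it in another. The 50 is described as what is needed to reject the null hypothesis, so it should be a number analysed. The recruitment commitment is a number implanted. Between the two, the plan names several ways to leave, turns early leavers and patients with incomplete baseline data into exclusions, and allows nothing for them. A study that implanted exactly 50 would comply with the protocol and could still analyse fewer than the protocol says it needs.

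Section 10.6 is the only analysis set defined. On its face it therefore governs procedure time, adverse events and revisions as well as paresthesia coverage, and any shortfall would reach every comparison.

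**Working it through.** **The plan's own figure.** The 50 can be neither reproduced nor refuted. Section 10.2 does not give the power, the SD of procedure time, or the endpoint that drove the simulations. It is taken here as stated. What can be checked is whether the rules deliver 50 analysed.

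**Inputs from the documents.** Minimum 50, 1:1, 5% level (10.2); 50 implanted satisfies 3.1; cap 30 per arm (6); completer analysis set (10.6); procedure time 60 versus 90 minutes, a difference of 30 (Table 2); two-sided t-test (10.3.1).

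**Assumptions.** The loss rate d, meaning the proportion of implanted patients who fall outside the 10.6 set, is not in the documents, so a range is shown. Losses are taken as independent. The SD is also not in the documents, and three values are shown.

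**Step 1. Chance of a shortfall if enrolment stops at 50.** P(fewer than 50 analysed) = 1 − (1 − d)^50, and the expected number analysed is 50(1 − d).

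| d | P(fewer than 50 analysed) | Expected analysed |
|---|---|---|
| 1% | 1 − 0.99^50 = 39% | 49.5 |
| 2% | 1 − 0.98^50 = 64% | 49 |
| 5% | 1 − 0.95^50 = 92% | 47.5 |
| 10% | 1 − 0.90^50 = 99.5% | 45 |

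The probability passes 95% at d = 1 − 0.05^(1/50), about 5.8%.

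**Step 2. The same at the cap.** With 60 implanted, 60 − 50 = 10 losses can be absorbed (16.7% of 60). The binomial probability of fewer than 50 analysed is 0.02% at d = 5%, 3.4% at 10% and 28% at 15%.

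**Step 3. Implants needed for an expected 25 analysed per arm.** 2 × ceil(25/(1 − d)):

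- 5%: 25/0.95 = 26.3, so 27 per arm, 54 in all.
- 10%: 25/0.90 = 27.8, so 28 per arm, 56 in all.
- 15%: 25/0.85 = 29.4, so 30 per arm, 60 in all, which is the cap.
- 20%: 25/0.80 = 31.25, so 32 per arm, above the cap.

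These numbers hold 50 only on average. With 54, 56 or 60 implanted at those first three rates, the chance of fewer than 50 analysed is still 13%, 33% or 28%.

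**Step 4. Power for procedure time.** Two-sided t-test at 5%, noncentral t with noncentrality 30/(SD × √(1/n1 + 1/n2)). At 25 + 25 and SD 37, for example, this is 30/(37 × √0.08) = 2.87.

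| Assumed SD (min) | 50 analysed (25 + 25) | 45 analysed (23 + 22) |
|---|---|---|
| 25 | 99% | 98% |
| 30 | 93% | 91% |
| 37 | 80% | 76% |

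The SD of 37 is the value at which 50 patients give about 80% power. It was chosen for that reason and has no source in the plan.

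**The case against.** The strongest reply is that 50 is a floor. Section 6 allows 60, and at 60 implanted a shortfall is rare for losses up to about 10% (Step 2). The no-replacement rule does not stop enrolment from continuing to the cap. This stands as far as it goes: the design has room for the losses. But a cap permits and does not commit. The plan does not offer the extra ten as a loss allowance, the summary speaks of about 50, and 3.1 is met at 50 implanted. The figure of ten also assumes that all 60 enrolled are implanted.

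A second reply is that the power cost is small and rests on an SD nobody has stated. That also stands. At an SD of 25 or 30 the change is one to three points.

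Three stronger readings are tempting and should not be drawn:

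- *A shortfall is almost certain.* This needs both enrolment stopping at 50 and a loss rate of several percent. The documents establish neither.
- *The 0% screen-failure assumption causes the shortfall.* The floor counts implanted patients, so failures before surgery cannot reduce it. The assumption matters here only because it is the one loss the section quantifies, and it is a different kind of loss.
- *Section 10.2 claims that no adjustment for attrition is needed.* It makes no such claim. It is silent on attrition, so there is nothing to delete.

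It can also be said that procedure time is recorded at surgery and needs no 6-week visit, and that exits after explant may be related to outcome. Both are fair, but they concern who belongs in the analysis set, which a larger sample would not settle.

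**Conclusion.** The point holds as an omission; no figure in the plan is shown to be miscalculated. Section 10.2 states a required minimum that the enrolment and analysis rules do not secure. At exactly 50 implanted, any loss at all takes the analysed number below it.

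The probabilities depend on the assumed loss rate and on independence. The power figures depend on the assumed SD, and at 10% loss the cost is between about one and four points over the SDs shown. The conclusion also reads 10.6 as limiting the analysis to the patients it describes, which is the natural reading since no other set is defined. The existing cap makes this easy to repair but does not repair it as written. It should be corrected; it does not undermine the design.

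**What to change.** In Section 10.2, state an assumed rate of loss between implantation and the 10.6 analysis set, then choose one of two wordings.

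1. Define 50 (25 per arm) as the number in the 10.6 analysis set, with enrolment continuing within the existing 30 per arm until it is reached. Add that continuing to the cap does not count as replacement under Section 11, and align the counts in Section 3.1 and the summary.
2. State that 50 is the number implanted, and give the smaller number expected in the analysis (about 45 at 10% loss) with its power and the SD assumed.

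The cost is wording and, under the second option, a slightly less favourable figure. The cap stays as it is. The first option may mean up to ten more implants and some delay in knowing when to stop: activation comes about 2 to 3 weeks after surgery and the visit 6 weeks after that, so completer status is known roughly 8 to 9 weeks after implantation. If the assumed loss is well above 15%, the cap itself would no longer suffice, and the section should say so.
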